TITLE: The impact of suctioning on oxygenation during RSI in the Emergency Department – A Multi-centre Pilot Study

Unique Protocol ID: 2020-01-32

Document Date: January 2, 2020

Introduction

Rapid Sequence Intubation (RSI) is a common procedure in Emergency Departments (ED). However, it is a high-risk procedure and has been associated with significant complications including hypoxia, hypotension, airway trauma, aspiration, and death (1-3). Specifically, hypoxic episodes during intubation can lead to poor outcomes such as dysrhythmias, haemodynamic compromise, hypoxic brain injury and cardiac arrest, and is therefore of primary concern during any intubation procedure (4,5). Aspiration is a serious adverse event and potential cause of hypoxia during RSI and can lead to poor patient outcomes downstream of the procedure. The reported incidence of aspiration during RSI in the ED ranges from 3 to 8% in the ED population (6,7). In order to achieve an optimal view of the glottis and prevent pulmonary aspiration of fluids in the oropharynx, providers apply suction prior to and during laryngoscopy, using a Yankauer or large bore suction catheter. (8).

There is currently significant variation in suctioning during laryngoscopy, with some providers using very little suction as needed to clear heavy fluids (judicious suctioning), while others utilise suction aggressively (lead with suction) and as a part of their routine laryngoscopy technique (9, 10, 11). Evidence suggests inline suction on already-intubated patients accelerates desaturation, but we are aware of no studies examining the impact suctioning has on the speed of desaturation during emergent endotracheal intubation (11,12).

This pilot study aims to compare the effects of intermittent, as-needed “judicious” suctioning versus aggressive “continuous” (lead with) suctioning on oxygenation during rapid sequence intubation in the emergency department.

Methods

Setting

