In order to enrol patients into this pilot study and to gain experience from International centres this study will be performed at 4 sites: the Royal Prince Alfred (RPA) Hospital Emergency Department, Sydney, Australia, Mount Sinai Hospital, Manhattan, NY, Maimonides Medical Center, Brooklyn, NY and NYC H+H/Lincoln Medical Centre, Bronx, New York, USA. The RPA Hospital is a Level 1 Trauma Centre with approximately 85,000 presentations and 240 intubations per year. Lincoln Medical Centre is a Level 1 Trauma Hospital with approximately 175,000 presentations and 450 intubations per year. Mount Sinai Hospital is a tertiary referral center whose ED sees approximately 125,000 patients per year with around 200 intubations. Maimonides Medical Center is a level 1 trauma center that treats about XXX and performs about XXX intubations per year.

Study Participants

All adult patients requiring emergent rapid sequence intubation (RSI) in the resuscitation bay will be included in the study. Patients that have a heavily soiled airway (i.e. secretions, vomitus, blood) as deemed by the physician requiring suction will be excluded.

Variables measured

The variables included in the study are shown on the Data collection sheet (Appendix 3) and will include the following:

- Patient details: Age, Gender, estimated weight
- Indication for RSI
- C-spine immobilisation and manual inline stabilisation
- Method of preoxygenation
- Method of apnoeic oxygenation, if performed
- Head up or supine position
- Oxygen saturation and ETO₂ prior to starting preoxygenation and at induction (completion of preoxygenation)
- Oxygen saturation and ETO₂ during procedure (at 10 second intervals starting with induction).
- Time of preoxygenation
- Induction medication and dose used
- Paralytic and dose used
- Induction time
- Endotracheal intubation time
- Method of intubation
- Number of attempts
- Cormack-Lehane grade of airway
- Use of cricoid or External laryngeal manipulation
- Continuous versus judicious suctioning

Intervention

The aim of this study is to investigate the effect of suctioning (a current technique used conventionally in RSI) on oxygenation levels during RSI. This being noted, there is no new intervention being applied to the patient.

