In order to investigate this, the current standard of care of suctioning will be used either by judicious means (i.e. in and out suction as needed) or continuous means (i.e. throughout the procedure, including laryngoscopy and tube placement) according to conventional practice at the discretion of the treating physician. For all patients involved in the study, there will be no new intervention applied. The impact of the use of suctioning, again which is standard of care and applied by convention, will be determined by measuring oxygen saturation as a primary outcome. All aspects of RSI will be at the discretion of the treating clinician, which is the current standard, including induction/relaxant medication, positioning of the patient, preoxygenation method, method of intubation and post-intubation sedation. At all institutions RSI is performed in a similar manner utilising an airway checklist (Appendix 1 and 2). However, there are no 'Standard Operating Procedures' for RSI in any ED and therefore intubation technique will vary depending on clinician preference and the clinical circumstances.

Once the decision to perform RSI has been made by the treating team, the patient will be enrolled into either a judicious or continuous suction group at random. In either case, suctioning will be applied to the patient as determined necessary by the clinician. Rapid sequence intubation will then be performed in the standard means by the treating provider.

Outcomes

Primary Outcome

The primary outcome of this study is the oxygen saturation achieved (SpO_2) at the time of tube placement (via confirmation with first ETCO_2 waveform) achieved during the intubation period.

Secondary Outcomes

The secondary outcomes measured include:

- Incidence of desaturation ($\text{SaO}_2 < 90\%$) or > 10 points from baseline during the intubation period
- Lowest O_2 saturations at any point during the intubation period
- The ETO_2 at induction and at ETT confirmation.
- Time from preoxygenation to endotracheal intubation
- Complications during RSI: bradycardia, tachycardia, hypotension, hypertension, oesophageal intubation, aspiration, airway or dental trauma, equipment or medication error
- Number of intubation attempts

Data Collection

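### Should lowest SpO2, rather than one reading at tube confirmation, be the primary outcome?

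*Combined protocol and SAP*

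**What the plan says.** The Primary Outcome section fixes one time point: "The primary outcome of this study is the oxygen saturation achieved (SpO_2) at the time of tube placement", established by the first ETCO2 waveform. The closing words of that sentence mention the intubation period, but the parenthesis sets the moment.

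The Secondary Outcomes section adds two measures that cover the whole course: "Incidence of desaturation" (SaO2 below 90%, or a fall of more than 10 points from baseline) and the lowest "saturations at any point during the intubation period". It also lists "Number of intubation attempts" and, among complications, "oesophageal intubation, aspiration, airway or dental trauma".

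Under Variables measured, saturation is recorded "during procedure (at 10 second intervals starting with induction"; induction time and intubation time are recorded as well. Statistical Analysis gives a t-test for mean saturations and a chi-squared test for desaturation. Sample Size sets 100 patients, 50 per group, says that no calculation was possible, and assigns the data to planning a larger trial.

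**The concern.** The Introduction describes hypoxia during intubation in strong terms: it "is therefore of primary concern during any intubation procedure". An episode is an event over time, and a single reading at the end shows it only if it is still present then. Over a window that ends at confirmation, the lowest SpO2 can never exceed the confirmation value. The two differ exactly in patients who fell and then recovered, for example between attempts. The protocol expects such courses, because it records attempts and oesophageal intubation.

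If recovery is common, the primary comparison is pulled towards no difference while the secondary outcomes are not, and the planning figures for the later trial could be taken from the diluted measure. A patient with no confirmed tube would drop out of the t-test and might be among the most hypoxic. Lowest SpO2 comes from the same record, so exchanging the two outcomes looks free.

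**Working it through.** **What the plan's own figures allow.** The total of 100 has no alpha, power, SD or effect behind it, so there is nothing to reproduce. For scale, assume two-sided 5% and 80% power. The detectable difference with 50 per group is (1.960 + 0.842) × √(2/50) = 0.56 SD, which is 2.8 points at SD 5 and 5.6 points at SD 10.

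**More than one attempt.** The outcome is tied to the confirming waveform. However many attempts precede it, the value is the SpO2 at that waveform. Scoring is therefore defined, and only the unconfirmed tube lacks a rule.

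**Sensitivity without artefact.** All inputs except 50 per arm are assumptions:
- SpO2 = 99 − G, with G gamma (shape 0.8, mean 7 in one arm and 11 in the other), clipped to 40–100.
- A share p of patients who fall below 90% is re-oxygenated to 96% before the final attempt, as are 10% of the others (none when p = 0).
- Two-sample t-test at 5%, 10,000 replicates (standard error of a power figure about √(0.25/10,000) = 0.5 percentage points).
- Model A: no further fall after re-oxygenation. Model B: the final attempt brings a new fall from the same arm's distribution, which fits suction used "throughout the procedure, including laryngoscopy and tube placement" in the continuous group.

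| p | A: difference at confirmation | A: power, confirmation v lowest | B: difference, confirmation v lowest | B: power, confirmation v lowest |
|---|---|---|---|---|
| 0% | 3.9 | 50 v 50% | 3.9 v 3.9 | 50 v 50% |
| 10% | 3.5 | 44 v 49% | 3.9 v 4.1 | 49 v 51% |
| 20% | 3.2 | 39 v 50% | 3.8 v 4.2 | 49 v 52% |
| 30% | 2.7 | 32 v 50% | 3.7 v 4.3 | 48 v 53% |
| 50% | 2.0 | 23 v 50% | 3.4 v 4.5 | 46 v 54% |

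The lowest-SpO2 difference in model A stays at about 3.9 points. At p = 0 the measures coincide. Large losses arise only in model A. In model B, up to p = 30%, the gap is 2 to 5 percentage points.

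**Sensitivity with artefact.** A minimum over many readings picks up any spurious low value, whereas a single reading is exposed once. Further assumptions: 12 readings per patient including the one at confirmation; each is spuriously low with the stated probability; artefact values are uniform on 60–90%; no filtering. Power, confirmation v lowest:

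| p | A, 0.5% | A, 1% | B, 0.5% | B, 1% |
|---|---|---|---|---|
| 0% | 49 v 40% | 47 v 35% | 49 v 41% | 47 v 35% |
| 10% | 42 v 41% | 42 v 35% | 48 v 43% | 48 v 38% |
| 20% | 37 v 41% | 37 v 35% | 48 v 45% | 47 v 39% |
| 30% | 32 v 41% | 31 v 36% | 46 v 45% | 46 v 40% |
| 50% | 22 v 42% | 22 v 35% | 45 v 47% | 44 v 41% |

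The ordering reverses when re-oxygenation is infrequent. In model B at 1% artefact it is reversed throughout. In model A, lowest SpO2 still does better once p is high (from 20% at 0.5% artefact, from 30% at 1%).

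**No confirmed tube.** At a true difference of 0.56 SD, power falls from 80% to 78% with 48 per group and to 76% with 45. Imbalance could bias the result. With 4/50 against 1/50 such patients, at an assumed 75% against 94% for the rest, the means differ by (0.08 − 0.02) × 19 = 1.1 points, which is lost if those patients are dropped. These counts are invented for illustration; the documents give none.

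**The case for a change.** The best case for change is that lowest SpO2 matches the stated worry about hypoxic episodes, needs no new data, and without artefact is never the weaker measure. In model B at p = 50%, 27% of hypoxic patients in the better arm and 21% in the worse arm read 90% or more at confirmation. An artefact rule set in advance would remove much of the penalty shown above. The pilot also feeds a later trial, and the plan does not say which outcome will supply its variance.

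Part of this stands. A single reading at confirmation does miss recovered episodes, and the value for an unconfirmed tube is unstated. But the advantage of lowest SpO2 needs either appreciable recovery or clean readings, and the documents establish neither. Readings are written on a sheet by clinical staff during an emergency procedure, so some artefact is plausible. Confirmation is also one fixed event, the same for every patient. The stated aim is the effect on oxygenation during intubation, which either measure serves. The Sample Size section does not tie later planning to the primary outcome, and both sets of data will be in hand.

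**Conclusion.** No change is called for. The primary outcome is a defensible choice whose known blind spot is covered by two prespecified secondary outcomes, one of them with its own test. Depending on assumed rates, the power difference runs from 27 percentage points in favour of lowest SpO2 (model A, half of hypoxic patients recovering, no artefact) to about 12 in favour of confirmation (no recovery, 1% artefact). It is zero with neither recovery nor artefact. That range does not show that the plan chose the worse measure, and the pilot claims no power for either.

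The rest is detail of the kind analysts fill sensibly. Patients without a confirmed tube can be counted by arm and described from their serial readings. The intubation period has a natural start at induction, where the 10-second record begins, and a natural end at confirmation. Any definition on the data collection sheet (Appendix 3) cannot be seen in the text available. Reporting lowest SpO2 beside the primary result already follows from its place among the outcomes.

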The data will be collected prospectively during the time of RSI by nursing and medical staff with the use of a data collection sheet (Appendix 3). Staff at RPA ED are familiar with the data collection sheets as prior studies in relation to RSI have been performed previously (Study number Re: X12- 0394). Similarly staff at Lincoln Medical centre and Mount Sinai perform routine data collection on all RSI's performed in the ED for quality improvement purposes. The staff at Maimonides and Mount Sinai will be trained in the procedure for collecting data with the use of the data collection sheets.

Patient risk

This study investigates the effect of providing suction during RSI on SpO₂ levels. This study will have no direct impact on patient care as it evaluates the use of a current accepted standard in the ED. This adds to clinical information and may lead to either no change or improved patient care. There are no risks to the patient as the patient will be receiving standard of care in both arms of the study. Patients will be critically ill requiring an emergency procedure and therefore, consent is not necessary for this study as per the criteria of the Common Rule for waiver of informed consent for emergency research.

Sample Size

A sample size calculation for this study is not possible as this is a pilot study and there is currently no reported data on the impact suctioning has on oxygen saturation during RSI in emergency department patients. For this reason we have decided to perform a convenience sample of 100 patients (50 in the judicious group and 50 in the continuous group). Data from this study will be used to provide statistics for a sample size and power calculation for a larger randomized control trial in the future.

Statistical Analysis

Descriptive statistics will be used for the cohorts. Means with 95% confidence intervals and medians with interquartile range will be used to describe the cohorts. Chi squared test will be used to compare the proportion of patients that experience desaturation between the cohorts. A simple student's t-test will be used to compare the mean oxygen saturations and end tidal oxygen levels measured between the cohorts.

Study Endpoints

The endpoint for this pilot study will be the enrollment of 50 patients in each group to a total of 100 patients.

References

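### ETO2 at induction, a reading before laryngoscopy, is listed as a secondary outcome, and the only ETO2 comparison is an unadjusted t-test that leaves the pre-preoxygenation reading unused

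*Combined protocol and SAP*

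**What the plan says.** The Secondary Outcomes list gives one ETO2 item with two time points: "The ETO_2 at induction and at ETT confirmation". Under Variables measured, ETO2 and oxygen saturation are recorded "prior to starting preoxygenation and at induction (completion of preoxygenation", and again "during procedure (at 10 second intervals starting with induction". The plan therefore holds a reading before preoxygenation, one at its completion, and a series from then on.

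The Intervention section describes continuous suction as applied "throughout the procedure, including laryngoscopy and tube placement". It says that, once the decision to perform RSI is made, "the patient will be enrolled into either a judicious or continuous suction group at random". It also says "All aspects of RSI will be at the discretion of the treating clinician", and it names the preoxygenation method among these aspects. No blinding is described.

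For ETO2, the Statistical Analysis section gives one between-group method, a Student's t-test to "compare the mean oxygen saturations and end tidal oxygen levels measured between the cohorts". It names no time point, covariate or change score. It also states "Descriptive statistics will be used for the cohorts", with means and 95% confidence intervals, and medians and interquartile ranges.

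**The concern.** A reading taken as preoxygenation ends mainly measures how well preoxygenation worked. The two suction strategies should differ mostly later, during laryngoscopy and tube placement. Listed as an outcome and covered by a t-test with no time point, the induction reading could show a difference that arose by chance or from preoxygenation practice and then be reported as an effect of suction.

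In addition, an earlier ETO2 value is collected for each patient but enters no planned comparison. If it predicts ETO2 at tube confirmation, leaving it out widens the confidence interval for no saving in data collection. The Sample Size section says the pilot is meant to supply statistics for planning a larger trial. An adjusted SD and the correlation between the earlier and later readings would serve that purpose, and a t-test alone gives neither.

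**Working it through.** **Inputs.** The Sample Size section gives 50 patients per group (50 + 50 = 100). The documents give no SD, correlation or alpha, so there is no power figure to reproduce. I assume a two-sided 5% level and a correlation r between covariate and outcome of 0.1, 0.3 or 0.5. Differences are in SD units.

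**Order of events.** From Variables measured and Intervention: reading before preoxygenation; preoxygenation; reading at induction; laryngoscopy and tube placement; reading at confirmation. Allocation follows the decision to perform RSI, but its place relative to preoxygenation is not stated. The induction reading is thus before laryngoscopy, but it is not shown to be before allocation.

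**Precision.** The ratio of ANCOVA to t-test interval width is √(1 − r²) in large samples. Allowing for expected covariate imbalance and for 97 rather than 98 degrees of freedom, it is √[(1 − r²)(1 + 1/96)] × t97/t98. The equivalent sample size per group is 50/(1 − r²).

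| r (assumed) | Large-sample ratio | Ratio at 50 per group | CI narrower by | Equivalent n per group |
|---|---|---|---|---|
| 0.1 | 0.995 | 1.000 | about 0% | 50.5 |
| 0.3 | 0.954 | 0.959 | about 4% | 54.9 |
| 0.5 | 0.866 | 0.871 | about 13% | 66.7 |

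A simulation of 20,000 trials per value of r gave ratios of 1.000, 0.959 and 0.870, with type I error of 4.7% to 5.0% for both methods.

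**Chance imbalance.** The SE of a difference in means is √(2/50) = 0.20 SD. The median absolute imbalance in the covariate is 0.6745 × 0.20 = 0.135 SD, and the 95% limit is 1.96 × 0.20 = 0.39 SD. The unadjusted comparison shifts by r times the imbalance. For r = 0.3 and 0.5 this is 0.04 and 0.07 SD typically, and 0.12 and 0.20 SD at the limit. These shifts average to zero over randomisation.

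**What the adjustment does not do.** Suppose knowledge of the group shifted ETO2 at induction by 0.3 SD, and a fraction of 0.3 or 0.5 carried over to confirmation (both assumed). The confirmation comparison would move by 0.3 × 0.3 = 0.09 SD or 0.5 × 0.3 = 0.15 SD. The pre-preoxygenation reading is taken before such a shift can arise, so adjusting for it removes none of it. Adjusting for the induction reading removes r × shift; for a 0.2 SD shift that is 0.06 SD (r = 0.3) or 0.10 SD (r = 0.5). If allocation caused the shift, that model no longer estimates the overall difference between the allocated groups.

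**Missing covariate.** With a fraction m missing, complete-case ANCOVA has variance (1 − r²)/(1 − m) relative to the t-test, which equals 1 at m = r²: 1%, 9% or 25% for r = 0.1, 0.3 or 0.5. With 20% missing at random, mean imputation with a missing indicator gave simulated width ratios of 0.973 (r = 0.3) and 0.903 (r = 0.5), so about 3% and 10% narrower, with type I error of 4.7% to 4.9%.

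**The case against.** The strongest reply is that this is a refinement. The t-test is valid under randomisation, the outcome is secondary, and the pilot makes no power claim. The two time points may simply mark the start and end of the interval over which ETO2 falls. The descriptive statistics could already supply a summary at induction, and the Introduction says suction is applied before as well as during laryngoscopy, so the induction reading could carry some suction effect. The larger precision gains are also more plausible for the induction reading than for the pre-preoxygenation reading, because preoxygenation comes between the latter and the outcome.

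Much of this stands and limits the point. It does not remove it: the t-test as worded covers the ETO2 levels measured, the induction reading is listed as an outcome, and the general descriptive text neither exempts that reading from testing nor adjusts for an earlier value.

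A reader might infer three stronger claims that the documents do not support:
- **A high false-positive rate at induction.** An assumed shift of 0.2 SD from preoxygenation would make the induction t-test significant in 17% of trials with no suction effect. Nothing in the documents indicates that such a shift occurs or how large it would be.
- **A multiplicity failure.** Testing both readings gives a 9.5% or 9.1% chance of at least one p < 0.05 under the null (r = 0.3 or 0.5). That is ordinary multiplicity among several secondary outcomes, not particular to ETO2.
- **A gain of 28%.** This needs r = 0.7, which has no support for the pre-preoxygenation value.

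**Conclusion.** The point holds, at modest size. The plan lists a mainly preoxygenation-driven reading as an outcome, gives it no separate role in the analysis, and leaves an earlier ETO2 reading unused. The cost is some precision and a risk of misinterpretation.

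A reader might infer that the t-test is biased. It is not: averaged over random allocation it keeps its 5% error rate. That statement rests on the random assignment described under Intervention being carried out. The same section also leaves the means of suctioning to the treating physician, and the two statements should be reconciled.

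The precision gain rests on an unknown correlation. It is about 0%, 4% or 13% for r = 0.1, 0.3 or 0.5, and is likely at the low end for the covariate recommended here. Nor should a reader infer that adjustment cures arm-aware preoxygenation; any carry-over stays in the comparison. The same baseline adjustment could be applied to the primary SpO2 comparison, whose pre-preoxygenation reading is also listed as collected.

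**What to change.** - Keep ETO2 at tube confirmation as the secondary outcome for comparison.
- Report ETO2 at induction by group, with its mean difference and 95% CI, as a check on preoxygenation balance, and state that it will not be interpreted as a suction effect. At 50 per group the interval extends about 0.39 SD either side, so the check can show a large imbalance but cannot exclude a modest one.
- Analyse ETO2 at tube confirmation by ANCOVA with the pre-preoxygenation ETO2 as covariate. Keep patients who lack that reading by mean imputation with a missing indicator, on the condition that missingness does not depend on the group.
- Label any model adjusted for ETO2 at induction as supportive only, because that reading may follow an unblinded allocation. State when allocation is made known relative to preoxygenation.
- Consider the same adjustment for the primary SpO2 comparison.

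The cost is a few sentences and one extra model (two if the supportive model is run), using readings already on the collection list. The downside is that there may be no gain if r is near 0.1.

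### The complications outcome names ten items but not cardiac arrest or death, both of which the Introduction gives as harms, so the by-arm summary could omit the gravest events.

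*Combined protocol and SAP*

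**What the plan says.** The complications item under Secondary Outcomes reads "Complications during RSI: bradycardia, tachycardia, hypotension, hypertension, oesophageal intubation, aspiration, airway or dental trauma, equipment or medication error". Taking airway and dental trauma, and equipment and medication error, as separate items, it names ten. It has no category for other events. The line that introduces the secondary outcomes is "The secondary outcomes measured include".

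The Introduction says that RSI has been associated with "significant complications including hypoxia, hypotension, airway trauma, aspiration, and death". It then says that "hypoxic episodes during intubation can lead to poor outcomes such as dysrhythmias, haemodynamic compromise, hypoxic brain injury and cardiac arrest", and gives this as the reason hypoxia is the main worry during intubation.

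The Variables measured section opens with "The variables included in the study are shown on the Data collection sheet (Appendix 3) and will include the following". Its bullets ask for saturation and ETO₂ "prior to starting preoxygenation and at induction (completion of preoxygenation", and every 10 seconds after that. They print no heart rate, blood pressure, arrest or vital status.

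The Statistical Analysis section assigns a chi-squared test to desaturation and a t-test to saturation and ETO₂. It names no test for complications.

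**The concern.** The Introduction justifies the study partly by severe harms, and the outcome list has no place for two of them. An arrest during laryngoscopy would appear only through milder items, which do not separate it from a short-lived fall in heart rate or pressure. A death soon after tube placement would match no listed outcome.

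This bears on patient safety. Patients enter without consent under an emergency research waiver, and the Patient risk section states that taking part carries no risk. A by-arm count of the gravest events is the most direct check on that statement. The pilot is also meant to inform a larger randomised trial, whose planners will want to know whether such events occurred and in which group.

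A lesser worry concerns bradycardia, tachycardia, hypotension and hypertension. They have no printed threshold, onset rule or pre-induction value, and the patients are critically ill. Some will already meet any reasonable definition before induction.

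**Working it through.** The documents give no event rate, effect size or power for complications, and they describe the 100 patients (50 per group) as a convenience sample. There is no planned figure to reproduce. The check is mainly a comparison of sections, followed by illustrations on assumed rates.

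**1. Harms named against outcomes listed**

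| Harm named in the Introduction | Place in the printed outcomes |
|---|---|
| Hypoxia | Primary outcome, desaturation, lowest saturation |
| Hypotension, haemodynamic compromise | Hypotension, hypertension |
| Airway trauma | Airway or dental trauma |
| Aspiration | Aspiration |
| Dysrhythmias | In part: bradycardia, tachycardia |
| Hypoxic brain injury | None (unlikely to be assessable in the ED) |
| Cardiac arrest | None |
| Death | None |

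Arrest and death are the two harms that are both readily observed in the ED and without any item.

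**2. How many arrests might occur** (rates are assumptions)

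Expected number = 100p. Chance of at least one = 1 − (1 − p)^100.

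| p | Expected in 100 | Chance of at least one |
|---|---|---|
| 0.5% | 0.5 | 39% |
| 1% | 1 | 63% |
| 2% | 2 | 87% |
| 4% | 4 | 98% |

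**3. Could the arms be compared?**

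Take the most extreme split at the top of this range, 4 arrests against 0. Two-sided Fisher p = 2 × C(50,4)/C(100,4) = 2 × 230,300/3,921,225 = 0.12. With no arrests in an arm of 50, the one-sided 95% upper limit is 1 − 0.05^(1/50) = 5.8%. Counts by arm can be described but not usefully tested.

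**4. Haemodynamic items, if pre-existing abnormality is counted** (rates are assumptions)

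Let b be the proportion abnormal before induction and x the rate of new abnormality among the rest. The share of counted events already present is b/(b + (1 − b)x).

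| b | x | Share already present |
|---|---|---|
| 20% | 10% | 0.20/0.28 = 71% |
| 30% | 10% | 0.30/0.37 = 81% |
| 40% | 10% | 0.40/0.46 = 87% |
| 20% | 30% | 0.20/0.44 = 45% |
| 10% | 30% | 0.10/0.37 = 27% |

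The share runs from 27% to 87% over these inputs, so the documents cannot settle its size.

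The counted difference between arms is (1 − b) times the difference in new events. With new-event rates of 10% and 25%, a 15-point difference becomes 0.9 × 15 = 13.5 points at b = 10%, 12.0 at 20% and 10.5 at 30%.

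**The case against.** The strongest reply is that neither list claims to be complete. Both introductory lines use a form of the word include. The printed variables also leave out aspiration, oesophageal intubation, trauma and error, all of which are outcomes, so those bullets cannot be the whole of Appendix 3. The sheet may well record arrest, death, heart rate and blood pressure. This stands, and it rules out any claim that these data will not be collected. It does not remove the gap, because a box on a form does not make an event a prespecified outcome to be reported by arm.

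A second reply is that an arresting patient who desaturates is still counted, under desaturation and lowest saturation as well as bradycardia or hypotension. This is correct. The patient is not lost, but the arrest is not identified.

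A third is that a complication of a procedure ordinarily means something new. A reader might infer that the plan counts pre-existing shock as harm, but the text does not say so. It leaves the rule undefined, in contrast to desaturation, which can be met by a change of "or > 10 points from baseline during the intubation period". The missing thresholds and onset rule are mostly missing detail.

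A fourth is that the plan tests no complication and proposes no conclusion about them. That also stands, and it limits the consequence to what the descriptive summary contains.

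**Conclusion.** The point holds in a limited form. Cardiac arrest and death appear in no printed outcome or variable, although the Introduction names both as harms, so the complication summary could omit the gravest events. If the arrest rate is 1-4%, this would affect about 1-4 patients in 100. That range is an assumption. The case for change does not depend on it, since even one such event should be reported by arm.

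A reader might infer several stronger things that the documents do not support:

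- That death is given as a reason hypoxia matters. The Introduction lists death as a complication of RSI and ties only cardiac arrest to hypoxia.
- That the list is closed. Its wording is open, and Appendix 3 was not seen.
- That most haemodynamic events would describe illness on arrival. The share depends on assumed rates and falls to 27% under some of them.
- That one arm would be favoured. Under the random enrolment stated in the Intervention section, counting pre-existing states dilutes the contrast but does not push it systematically in one direction. Chance imbalance remains possible with 50 per arm.

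This is a cheap improvement to safety reporting and does not undermine the primary outcome.

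**What to change.** **Main change.** Add cardiac arrest and death to the complications outcome and, if they are not already there, to the data collection sheet. Count both from induction to a stated point after tube confirmation. The sponsor should choose that point; until the patient leaves the ED is one option. Report the counts by arm descriptively, and say that no between-arm test will be done because few events are expected.

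**Lesser change, if Appendix 3 does not already cover it.** Record heart rate and blood pressure just before induction. Count the four haemodynamic events only when they are new relative to those values, using one definition at all four sites.

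**Cost.** Two more items on the sheet, one set of pre-induction vital signs, agreement on a common definition, and matching protocol wording. Data are now collected at the time of RSI, so the window for arrest and death needs a short follow-up beyond it. Haemodynamic counts may be lower, but they will be easier to interpret. Patient care does not change.
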